3. POST-MONTH 6 STAGE : to assess the relative risk of symptomatic COVID-19 and of severe COVID-19 after the Month 6 dose in Group 1 (PLWH who are SARS-CoV-2 negative at baseline) and Group 2 (PLWH who are SARS-CoV-2 positive at baseline), separately and combined, among those who received mRNA-1273 at Month 6 vs. those who received mRNA-1273.222 at Month 6, counting endpoints at least 14 days after the Month 6 dose until end of follow up.	COVID-19 and severe COVID-19 as defined for the primary endpoints
4. POST-MONTH 6 STAGE : to assess the relative risk of virologically confirmed symptomatic COVID-19 and of severe COVID-19 after the Month 6 dose in Groups 1 and 3 together (participants who are SARS-CoV-2 negative at baseline regardless of HIV status) and in Groups 2 and 4 together (participants who are SARS-CoV-2 positive at baseline regardless of HIV status), respectively, among those who received mRNA-1273 at Month 6 vs. those who received mRNA-1273.222 at Month 6, counting endpoints at least 14 days after Month 6 dose until the end of follow up.	COVID-19 and severe COVID-19 as defined for the primary endpoints
5. PRE-MONTH 6 & POST-MONTH 6 STAGES : to assess the relative risk of symptomatic COVID-19 and of severe COVID-19 after the Month 6 dose by neutralization phenotype and Spike sequence features of acquired SARS-CoV-2 viruses (sieve analysis) in Groups 1 and 3 together (participants who are SARS-CoV-2 negative at baseline regardless of HIV status) and in Groups 2 and 4 together (participants who are SARS-CoV-2 positive at baseline regardless of HIV status), respectively, among those who received mRNA-1273 at Month 6 vs. those who received mRNA-1273.222 at Month 6, counting endpoints starting 1 day after dose 1, 14 days after the last pre-Month6 dose , or 14 days after Month 6 dose until the end of follow up.	COVID-19 and severe COVID-19 as defined for the primary endpoints; neutralization phenotypes and viral genotypic characteristics of SARS-CoV-2 at diagnosis.

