6. PRE-MONTH 6 & POST-MONTH 6 STAGES : to assess the relative risk of SARS-CoV-2 infection defined by nucleocapsid protein seroconversion regardless of symptomology after the Month 6 dose in Group 1 (PLWH who are SARS-CoV-2 negative at baseline) and in Group 3 (people HIV-negative who are SARS-CoV-2 negative at baseline) combined, among those who received mRNA-1273 at Month 6 vs. those who received mRNA-1273.222 at Month 6, counting endpoints starting 1 day after dose 1, 14 days after the last pre-Month 6 dose , or 14 days after Month 6 dose until the end of follow up.	SARS-CoV-2 infection diagnosed by seroconversion throughout the study.

Secondary Objectives	Secondary Endpoints
7. PRE-MONTH 6 & POST-MONTH 6 STAGES: to assess the relative risk of asymptomatic SARS-CoV-2 infection defined by nucleocapsid protein seroconversion after the Month 6 dose in Group 1 (PLWH who are SARS-CoV-2 negative at baseline) and in Group 3 (people HIV-negative who are SARS-CoV-2 negative at baseline) combined, among those who received mRNA-1273 at Month 6 vs. those who received mRNA-1273.222 at Month 6, counting endpoints starting 1 day after dose 1, 14 days after the last dose before Month 6 dose, or 14 days after Month 6 dose until the end of follow up.	SARS-CoV-2 infection diagnosed by seroconversion in the absence of symptoms.
8. PRE-MONTH 6 & POST-MONTH 6 STAGES: to assess the relative risk of symptomatic COVID-19, and severe COVID-19 after the Month 6 dose in Groups 1 and 3 together (participants who are SARS-CoV-2 negative at baseline regardless of HIV status) and in Groups 2 and 4 together (participants who are SARS-CoV-2 positive at baseline regardless of HIV status), respectively, among those who received mRNA-1273 at Month 6 vs. those who received mRNA-1273.222 at Month 6, counting endpoints starting 1 day after dose 1 or 14 days after the last dose before Month 6 dose until the end of follow up.	COVID-19 and severe COVID-19 as defined above
9. To assess post-vaccination immune response markers and immune markers as correlates of risk of COVID-19 and as correlates of protection against COVID-19 in all study groups together.	SARS-CoV-2-specific neutralization antibody, binding antibody and cellular immune responses

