## 6.3 Accrual and sample size

This study will enroll up to 15,600 participants into four groups defined by baseline HIV-1 and SARS-CoV-2 sero-statuses and randomized to receive the same vaccination series of mRNA-1273 at month 0 and month 1 (if applicable), but two different vaccines (mRNA-1273 or mRNA-1273.222) at month 6 at a 1:1 randomization ratio within each group as shown in the study schema. The sample sizes of Groups 1 and 2 are driven by the total number of COVID-19 cases that are needed to achieve sufficient statistical power to evaluate the relative risk of COVID-19 between Groups 1 and 2 in the pre-Month 6 stage, as well as between randomized interventions at Month 6 within each group in the post-Month 6 stage. The sample sizes of Groups 3 and 4 are primarily driven by the precision to characterize safety and immunogenicity of the regimens in each group of participants while keeping the same 1:2 ratio between the SARS-CoV-2 negative and positive groups as for Groups 1 and 2.

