Target population	Participants randomized to monovalent or bivalent under Protocol Version 6 (RM6)
Endpoint	COVE-/CDC-based COVID-19 endpoints counted 14 days after M6 vaccination
Time frame	13 days post M6 vaccination to M12/M18 visit
	Primary analysis II (applicable when # COVID-19 endpoints is at least 20)
Target population	Full per-protocol participants randomized to monovalent or bivalent under Protocol Version 6 (FPP)
Endpoint	COVE-/CDC-based COVID-19 endpoints counted 14 days after M6 vaccination
Time frame	13 days post M6 vaccination to M12/M18 visit
	Primary analysis III (applicable when # severe endpoints is at least 7)
Target population	Participants randomized to monovalent or bivalent under Protocol Version 6 (RM6)
Endpoint	Severe COVID-19 endpoints counted 14 days after M6 vaccination
Time frame	13 days post M6 vaccination to M12/M18 visit
	Primary analysis IV (applicable when # severe endpoints is at least 7)
Target population	Full per-protocol participants randomized to monovalent or bivalent under Protocol Version 6 (FPP)
Endpoint	Severe COVID-19 endpoints counted 14 days after M6 vaccination
Time frame	13 days post M6 vaccination to M12/M18 visit
	Secondary analysis I (applicable when # COVID-19 endpoints is at least 20)
Target population	Participants randomized to monovalent or bivalent under Protocol Version 6 (RM6)
Endpoint	COVE-/CDC-based COVID-19 endpoints counted 1 day after M6 vaccination
Time frame	M6 vaccination to M12/M18 visit
	Secondary analysis II (applicable when # severe endpoints is at least 7)
Target population	Participants randomized to monovalent or bivalent under Protocol Version 6 (RM6)
Endpoint	Severe COVID-19 endpoints counted 1 day after M6 vaccination
Time frame	M6 vaccination to M12/M18 visit
	Secondary analysis III
Target population	PLWH/PLWoH randomized to monovalent or bivalent under Protocol Version 6 (RM6)
Endpoint	COVE-/CDC-based/Severe (when applicable) COVID-19 endpoints counted 14 days after M6 vaccination
Time frame	13 days post M6 vaccination to M12/M18 visit
	Secondary analysis IV
Target population	PLWH/PLWoH randomized to monovalent or bivalent under Protocol Version 6 (RM6)
Endpoint	COVE-/CDC-based/Severe (when applicable) COVID-19 endpoints counted 1 day after M6 vaccination
Time frame	M6 vaccination to M12/M18 visit
	Secondary analysis V
Target population	Full per-protocol PLWH/PLWoH randomized to monovalent or bivalent under Protocol Version 6 (FPP)

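### Secondary objective 8 compares the two Month 6 vaccines but counts endpoints only from starts before the Month 6 dose, and objectives 5–7 do not say which start applies to that comparison

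*Protocol*

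**What the plan says.** **Objective 8 (Protocol Section 3).** The contrast is between recipients of the two Month 6 vaccines. The risk is described as "severe COVID-19 after the Month 6 dose in Groups 1 and 3 together", and likewise for Groups 2 and 4 together. The window is "counting endpoints starting 1 day after dose 1 or 14 days after the last dose before Month 6 dose", and it runs to the end of follow-up. No start after the Month 6 dose is offered.

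**Objectives 5–7 (same section).** The contrast is the same, but there are three alternative starts. Objective 5 begins "counting endpoints starting 1 day after dose 1, 14 days after the last pre-Month6 dose" and then adds a third start, 14 days after the Month 6 dose. Objective 6 ends "14 days after the last pre-Month 6 dose , or 14 days after Month 6 dose until the end of follow up", and objective 7 is alike. Objective 5 is a sieve analysis, split by baseline SARS-CoV-2 status. Objectives 6 and 7 use nucleocapsid seroconversion in Groups 1 and 3 only.

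**Treatment before Month 6 (Protocol Section 6.3).** Participants are randomized to "receive the same vaccination series of mRNA-1273 at month 0 and month 1 (if applicable"), then to one of two vaccines at Month 6, "at a 1:1 randomization ratio within each group".

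**Time zero (Protocol Section 6.4.3).** It is enrollment for pre-Month 6 objectives and the Month 6 dose for post-Month 6 objectives. None is given for objectives 5–8, which are headed for both stages.

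**SAP.** Section 4 starts the primary and secondary comparisons at the Month 6 vaccination or 13 days after it. Table 2 accordingly specifies "COVE-/CDC-based COVID-19 endpoints counted 14 days after M6 vaccination". Section 8.2.1 uses the Month 6 vaccination date for the exploratory comparison of the two vaccines. Enrollment is the origin only when baseline hybrid immunity is compared with vaccine immunity (Section 8.2.2).

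**The concern.** Until the Month 6 dose the two arms receive the same product on the same schedule. Events in that period say nothing about which Month 6 vaccine is better. Under randomization they fall equally on both arms, and adding equal numbers to each side of a ratio moves it toward 1. An analyst who followed objective 8 literally would therefore report a weaker vaccine contrast than the true one and could conclude that there is no difference when there is one.

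In objectives 5–7 the same outcome depends on which listed start the analyst picks. The SAP says that it addresses key secondary objectives of protocol Version 8.0, yet no analysis in it matches objective 8 as written. Either document can be followed only by departing from the other.

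**Working it through.** **1. The plan's own figure.** Protocol Table 6-2 (post-Month 6 stage) gives 87% power for a relative risk of 2.0 with 91 events, 2,000 per arm, exact binomial test, two-sided 0.05. Given the total, the mRNA-1273 share is 2/(1+2) = 0.667 against 0.5 under the null. The exact test gives 87.4%. The other five rows also reproduce: 54.1, 92.9, 98.7, 78.1 and 96.2% against the stated 54, 93, 99, 78 and 96%. These figures assume counting from Month 6.5, so the design itself uses the later start.

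**2. Inputs for the dilution.**
- Dose days 1, 29 (Groups 1 and 3) and 169 (Protocol Section 8.1), and Month 18 = Day 547 (Appendix K).
- The vaccine effect is taken to begin 14 days after the Month 6 dose, Day 169 + 14 = 183. From dose 1 there are 182 days with ratio 1, then 547 − 183 = 364 days with ratio 2.0.
- From 14 days after the last pre-Month 6 dose, the ratio-1 period is 183 − 43 = 140 days in Groups 1 and 3 and 183 − 15 = 168 days in Groups 2 and 4.
- Interim annual incidence before Month 6 (Section 2.1): 7.1% (Group 1), 2.2% (Group 2), 5.8% (Group 3), 1.5% (Group 4).
- Weights from the ceiling sizes in Table 1-1: Groups 1 and 3, (4,200×7.1 + 1,000×5.8)/5,200 = 6.85%; Groups 2 and 4, (8,400×2.2 + 2,000×1.5)/10,400 = 2.07%.
- Annual incidence after Month 6 in the mRNA-1273 arm: 2.5–3.5% (Section 6.3.1).

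**3. Formula.** Cumulative hazard H = (pre-rate × pre-time) + (post-rate × post-time). The post-rate is halved in the mRNA-1273.222 arm. Diluted ratio = [1 − exp(−H for mRNA-1273)] / [1 − exp(−H for mRNA-1273.222)].

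Example, Groups 1 and 3 at 3.0%: the pre-period contributes 0.0685×182/365.25 = 0.0341 to both arms. The post-period contributes 0.0299 and 0.0150. Ratio = (1 − e^−0.0640)/(1 − e^−0.0491) = 1.30.

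| Start of counting, true ratio 2.0, to Month 18 | Groups 1 and 3 | Groups 2 and 4 |
|---|---|---|
| 14 days after the Month 6 dose | 2.0 | 2.0 |
| 1 day after dose 1, interim rates | 1.26–1.33 | 1.54–1.62 |
| 14 days after last pre-Month 6 dose, interim rates | 1.31–1.39 | 1.56–1.63 |
| 14 days after last pre-Month 6 dose, constant incidence | (140+364)/(140+182) = 1.57 | (168+364)/(168+182) = 1.52 |

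At constant incidence, counting from dose 1 gives (182+364)/(182+182) = 1.50.

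**4. Sensitivity to the pre-Month 6 rate.** The planning assumptions in Section 6.3.1 (5% six-month incidence, 63% efficacy, half the background rate in Group 2) imply 3.7% a year in Group 1 and 1.85% in Group 2. Counting from dose 1 then gives 1.40–1.47 and 1.57–1.64.

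**5. Infection and sieve endpoints.** The documents give no seroconversion rate by arm and no rate by viral feature, so no size can be computed. SAP Tables 2 and 3 contain no infection comparison by Month 6 vaccine. Both definitions in SAP Section 6.3.1 are anchored to enrollment baseline, and Section 6.3.2 (asymptomatic infection) is still to be written.

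**The case against.** The strongest reply is that the starts are stage-specific shorthand. Objectives 5–8 are headed for both stages, and Protocol Section 6.4.3 links the early starts to the pre-Month 6 stage and the 14-day start to the Month 6 dose. For objectives 5–7 this is a plausible reading, although the text never says which start belongs to which contrast. It does not rescue objective 8: the only contrast there is between Month 6 vaccines, the window runs to the end of follow-up, and no post-Month 6 start is listed.

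Several stronger readings are tempting, and the documents do not support them.
- *Counting from dose 1 is required.* No objective requires it. Objective 8 offers a second start, and objectives 5–7 include the correct one.
- *The planned efficacy results are biased.* Every SAP comparison of the Month 6 vaccines for COVID-19 or severe COVID-19 starts at or after Month 6, as do primary objectives 3–4 and secondary objectives 3–4.
- *A single ratio and a power loss.* Pooling all four groups at 3.66% a year gives 4,000×0.0366×169/365 = 67.8 early events. Added to 76 or 106 later events, these give ratios of 1.43 or 1.51, and power falls from 78% to 51% or from 93% to 74%. None of these objectives pools all four groups, and the split of the 4,000 by group is not stated, so no power figure attaches to any objective.
- *An early start uniquely removes people with early events.* Section 6.4.3 also excludes anyone with an earlier endpoint when counting starts later.
- *The protocol rule is the only one for infection.* SAP Section 7 sets a general Month 6 origin for post-Month 6 analyses. What remains open is the missing infection comparison and the baseline-anchored definition.

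**Conclusion.** The concern holds as a fault in the protocol's counting rule and a mismatch with the SAP. Objective 8 contradicts itself: it names risk after the Month 6 dose and counts only from before it. Objectives 5–7 are ambiguous. Every early start biases the vaccine contrast toward 1.

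For symptomatic COVID-19 with a true ratio of 2.0, counting from dose 1 yields about 1.3 in Groups 1 and 3 and 1.5–1.6 in Groups 2 and 4. Objective 8's other start yields about 1.5–1.6 at constant incidence. Under the interim rates that start is no milder in Groups 1 and 3 than 1.31–1.39.

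These sizes assume constant hazards within each stage, equal dropout by arm, the planned group mix, and the same 2.5–3.5% annual incidence after Month 6 in every group. If incidence after Month 6 were higher in Groups 1 and 3, their dilution would be smaller. The direction does not depend on these assumptions.

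The primary analyses are unaffected. Infection objectives 6–7 are the most exposed, because the SAP has yet to specify their comparison.

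**What to change.** - **Objective 8:** delete it, because with a corrected window it has the same groups, endpoints and contrast as secondary objective 4. Alternatively, restate it as a comparison of baseline groups, for which counting from dose 1 makes sense.
- **Objectives 5–7:** state that any contrast between Month 6 vaccines counts only from 14 days after the Month 6 dose, with 1 day after as a supportive analysis. Keep the earlier starts for baseline-group comparisons, and say so.
- **Protocol Section 6.4.3:** give time zero for objectives that span both stages.
- **SAP:** when the infection comparison is added, use the same origin and re-base infection status at Month 6. SAP Section 5 already defines a Month 6 SARS-CoV-2 status from NAAT and central serology, with central serology expected for all participants at Month 6.

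The cost is protocol wording in four objectives and one section, plus one origin rule in the SAP. No new data are needed.

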## 4 Ethical considerations

It is critical that universally accepted ethical guidelines are followed at all sites involved in the conduct of clinical trials. The COVID-19 Prevention Network (CoVPN) have addressed ethical concerns in the following ways:

- CoVPN trials are designed and conducted to enhance the scientific knowledge base necessary to find a preventive vaccine, using methods that are scientifically rigorous and valid, and are in accordance with International Council for Harmonisation of Technical Requirements for Pharmaceuticals for Human Use (ICH) and/or other Good Clinical Practice (GCP) guidelines.
- CoVPN scientists and operational staff incorporate the philosophies underlying major codes (146-148), declarations, and other guidance documents relevant to human subjects research into the design and conduct of SARS-CoV-2 vaccine clinical trials.
- CoVPN scientists and operational staff are committed to substantive community input—into the planning, conduct, and follow-up of its research—to help ensure that locally appropriate cultural and linguistic needs of study populations are met.
- The CoVPN provides training so that all participating sites similarly ensure fair participant selection, protect the privacy of research participants, and obtain meaningful informed consent. During the study, participants will have their well-being monitored, and to the fullest extent possible, their privacy protected. Participants may withdraw from the study at any time.
- Prior to implementation, CoVPN trials are rigorously reviewed by scientists who are not involved in the conduct of the trials under consideration.
- CoVPN trials are reviewed by local and national regulatory bodies and are conducted in compliance with all applicable national and local regulations.
- The CoVPN designs its research to minimize risk and maximize benefit to both study participants and their local communities. For example, CoVPN protocols provide enhancement of participants' knowledge of SARS-CoV-2 and SARS-CoV-2 prevention, as well as counseling, guidance, and assistance with any social impacts that may result from research participation. CoVPN protocols also include careful medical review of each research participant's health conditions and reactions to study products while in the study.
- CoVPN research aims to benefit local communities by directly addressing the health and SARS-CoV-2 prevention needs of those communities and by strengthening the capacity of the communities through training, support, shared

knowledge, and equipment. Researchers involved in CoVPN trials are able to conduct other critical research in their local research settings.

- The CoVPN values the role of in-country Institutional Review Boards (IRBs), Ethics Committees (ECs), and other Regulatory Entities (REs) as custodians responsible for ensuring the ethical conduct of research in each setting.
- All participants will receive vaccine during this trial.
- If a participant is diagnosed with COVID-19 during the course of the study, country-specific guidelines on administration of vaccination if available will be followed.
- All participants with COVID-19 will receive the optimal local standard of care for prevention and treatment of COVID-19, including access to temperature monitoring, pulse oximetry, oxygen, medications such as steroids, and hospitalization at facilities that are both prepared and experienced at the management of severe cases to minimize mortality.
- All participants who are pregnant at any time during the study will be offered HIV counseling and testing if they are not known to be PLWH, and referral for prenatal and obstetrical care. All PLWH will be referred for HIV care if not already in a program.

## 5 IRB/EC review considerations

US FDA and other US federal regulations require IRBs/ECs/REs to ensure that certain requirements are satisfied on initial and continuing review of research (Title 45, Code of Federal Regulations (CFR), Part 46.111(a) 1-7; 21 CFR 56.111(a) 1-7). The following section highlights how this protocol addresses each of these research requirements. Each CoVPN Investigator welcomes IRB/EC/RE questions or concerns regarding these research requirements.

HCORE is paying for this study through funding to NIAID and the trial is being conducted in countries outside of the United States. Due to this, the trial is subject to both US and local regulations and guidelines on the protection of human research subjects and ethical research conduct. Where there is a conflict in regulations or guidelines, the CoVPN strives toward maximum protection of human research participants.

In compliance with international and local (as appropriate) ICH and/or other GCP guidelines, each research location has a locally based Principal Investigator (PI) who is qualified to conduct (and supervise the conduct of) the research. The investigators take responsibility for the conduct of the study, including obtaining all appropriate regulatory and ethical reviews of the research.

### 5.1 Minimized risks to participants

#### **45 CFR 46.111 (a) 1 and 21 CFR 56.111 (a) 1: Risks to subjects are minimized.**

This protocol minimizes risks to participants by (a) correctly and promptly informing participants about risks so that they can join in partnership with the researcher in recognizing and reporting harms; (b) respecting local/national blood draw limits; (c) performing direct observation of participants postvaccination; (d) having staff properly trained in administering study procedures that may cause physical harm or psychological distress, such as blood draws, vaccinations, COVID-19 testing and counseling; (e) providing safety monitoring; (f) ensuring any participant with COVID-19-like symptoms have access to optimal local standard of care for prevention of acquisition and treatment of COVID-19; and (g) participants are permitted to get vaccinated outside the study if they have access.

### 5.2 Reasonable risk/benefit balance

#### **45 CFR 46.111(a) 2 and 21 CFR 56.111(a) 2: Risks to subjects are reasonable in relation to anticipated benefits, if any, to subjects, and**

**the importance of the knowledge that may reasonably be expected to result.**

In all public health research, the risk-benefit ratio may be difficult to assess because the benefits to participants in prevention protocols are not as apparent as they would be in treatment protocols, where a study participant may be ill and may have exhausted all conventional treatment options. However, this protocol is designed to minimize the risks to participants while maximizing the potential value of the knowledge it is designed to generate.

